10.4.2. Analysis of the Primary Endpoint

The primary estimand is the difference between treatment groups in the proportion of participants with a ≥ 3 -step improvement from Baseline on the DRSS score at Week 24, among participants in the ITT Population. Participants who have missing data at the Week 24 time point will be considered non-responders. The proportion of participants with improvement at Week 24 will be compared among treatment groups using a Cochran-Mantel-Haenszel chi-square test, stratified by the DRSS category at Baseline (moderately severe or severe).

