10.4.3. Analysis of the Secondary Endpoints

Analysis of the secondary endpoints will be based on the ITT Population.

The proportion of participants with a \geq 2-step improvement from Baseline on the DRSS score at Week 24, as well as the proportion of participants progressing to CI-DME, PDR, and/or requiring ASNV requiring treatment, will be analyzed using a similar method as described for the primary endpoint.

Time to the event of CI-DME, PDR, and/or ASNV requiring treatment will be summarized using Kaplan-Meier (KM) methodology. Participants who do not experience the event will be censored at the time of their last non-missing evaluation. AKST4290 will be compared to placebo using the stratified log-rank test, stratified by the DRSS category at Baseline (moderately severe or severe). Kaplan-Meier estimates of the survival distribution function over time will be plotted by treatment group.

Clinical changes in diabetic kidney disease related laboratory values (e.g., eGFR and UACR) will be analyzed by a mixed-effects model for repeated measures (MMRM). The model will include fixed effects for treatment group, categorical visit, treatment group by visit interaction, the DRSS category at Baseline (moderately severe or severe), and the relevant Baseline value as a covariate. An appropriate covariance structure will be selected prior to database lock and the Kenward-Roger approximation will be used to calculate the denominator degrees of freedom for the test of fixed effects.

Safety will be assessed through summaries of AEs, changes in laboratory test results, and changes in vital sign measurements. In addition, all SAEs, including deaths, will be listed and summarized separately.

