10.4.6. Multiple Comparison/Multiplicity

The analysis of the single primary endpoint to compare AKST4290 with placebo will be evaluated at the 2-sided 5% level of significance. Analysis of secondary endpoints will be adjusted for multiple endpoint or treatment group comparisons. Analysis of any exploratory endpoints will be exploratory in nature and not based on any formal hypothesis testing. Details of all analyses will be provided in the SAP.

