10.5. Sample Size

Due to a dearth of studies with a 3-step improvement, as well as potential variabilities between each eye, the sample size is powered on the primary hypothesis comparing the difference between treatment arms (AKST4290 and placebo) in the proportion of participants with a ≥ 2 -step improvement of DR severity level on DRSS score in a single eye from Baseline as compared with Week 24. All calculations were based on the following fixed assumptions:

- Target 80% power.
- 2-sided alpha = 0.046.
 - It should be noted that to account for DSMB interim data reviews, the alpha spending approach has been adopted using an alpha reduction of 0.001 for each review (assuming a total of 4 reviews). The required sample size does not change if only three DSMB meetings are necessary.
- Test of 2 independent proportions based on the normal approximation.
- Based calculation on PANORAMA ([NCT02718326](#), [EYLEA Full Prescribing Information](#)), RISE/RIDE ([Nguyen 2012](#), [Wykoff 2018](#)), and VIVID/VISTA ([Korobelnik 2014](#), [Brown 2015](#)) study data.

The total sample size using the assumptions stipulated is approximately 80 enrolled participants to allow for a total of 69 completed participants. The randomization schema is 2:1 (AKST4290:placebo). Group sample sizes of 46 in the AKST4290 group and 23 in the placebo group will achieve approximately 80% power to detect a difference in group proportions of 24%. The proportion in the AKST4290 group is assumed to be 6% under the null hypothesis and 30% under the alternate hypothesis. The proportion in the placebo group is assumed to be 6%.

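### The stated 80% power for the ≥2-step endpoint does not describe the planned CMH test, which has roughly 64–75% at the same alpha

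*Protocol*

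**What the plan says.** Protocol 10.5 sizes the study on the ≥2-step endpoint, defined there as "improvement of DR severity level on DRSS score in a single eye from Baseline as compared with Week 24". It assumes 30% on AKST4290 and 6% on placebo, two-sided alpha 0.046 and 2:1 allocation, and concludes: "Group sample sizes of 46 in the AKST4290 group and 23 in the placebo group will achieve approximately 80% power to detect a difference" of 24 percentage points. The method is given as "Test of 2 independent proportions based on the normal approximation", without saying whether the variance is pooled. About 80 participants are to be enrolled so that 69 complete. SAP 4.5 repeats all of this.

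The analysis is described elsewhere. For the ≥2-step endpoint, Protocol 10.4.3 says "Analysis of the secondary endpoints will be based on the ITT Population" and that the proportion "will be analyzed using a similar method as described for the primary endpoint". In Protocol 10.4.2 that method is "compared among treatment groups using a Cochran-Mantel-Haenszel chi-square test, stratified by the DRSS category at Baseline (moderately severe or severe", with this rule for missing data: "Participants who have missing data at the Week 24 time point will be considered non-responders".

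On the significance level, Protocol 10.4.6 gives 5% to the single primary endpoint, which is ≥3-step improvement. For the rest it says "Analysis of secondary endpoints will be adjusted for multiple endpoint or treatment group comparisons", with no method or level named.

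**The concern.** A power statement should describe the test that will be run. A z-test with unpooled variance and a CMH test are close when the arms are equal in size and the rates moderate. They separate when the larger arm has the higher rate and the smaller arm has a rate near zero, as here. The unpooled formula gives the 23 placebo participants their own small variance, 0.06 × 0.94 = 0.0564. A null variance gives them the pooled value, 0.22 × 0.78 = 0.1716, about three times as large. Power computed the first way overstates the power of a test built the second way.

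The 80% is the only power figure in either document. If it does not carry over to the planned test, the risk of missing the assumed effect is understated, and anyone reusing the design inherits a sample size too small for its claimed power.

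**Working it through.** **Inputs from Protocol 10.5:** 30% and 6%; 46 and 23; two-sided alpha 0.046, so z = 1.995; 80 enrolled for 69 completers, so 11/80 = 13.75% lost. **Assumed, because the documents give no values:** the stratum splits, the rates within strata, an ITT split of 53/27, and missingness unrelated to response.

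**1. Reproducing the stated figure.** Unpooled z-formula:
- SE = √(0.30×0.70/46 + 0.06×0.94/23) = 0.0838
- Power = Φ(0.24/0.0838 − 1.995) = 80.8%

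The same formula solved for the placebo arm, (1.995 + 0.842)² × (0.06×0.94 + 0.30×0.70/2)/0.24², gives 22.55. At alpha 0.047 (three DSMB reviews) it gives 22.41. Both round up to 23, so N = 69, which agrees with the remark in 10.5 that three reviews would not change the sample size. That the sponsor used this form is an inference, but it fits the power, the N and that remark.

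**2. Other normal approximations, same inputs.**
- Pooled: p̄ = (46×0.30 + 23×0.06)/69 = 0.22; SE₀ = √(0.22×0.78×(1/46 + 1/23)) = 0.1058; power = Φ((0.24 − 1.995×0.1058)/0.0838) = 63.5%
- Arcsine: h = 0.664; power = Φ(0.664×√(46×23/69) − 1.995) = 72.8%

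**3. The planned test.** In stratum k, let a and b be the arm sizes, N = a + b, x the active responders and m all responders. CMH without continuity correction rejects when |Σ(x − am/N)| / √(Σ ab·m(N−m)/(N²(N−1))) ≥ z. Power is the summed binomial probability of every outcome that rejects.

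Splits (active/placebo):
- Completers: 23/12 + 23/11, 32/16 + 14/7, 36/18 + 10/5
- ITT: 27/13 + 26/14, 37/19 + 16/8, 42/21 + 11/6

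With missing counted as non-response, the rates become 0.30×69/80 = 25.9% and 0.06×69/80 = 5.2%.

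| Case | Completers 46/23 | ITT 53/27, 13.75% missing | ITT 53/27, none missing |
|---|---|---|---|
| Alpha 0.046, equal stratum rates | 66.0–66.9% | 64.4–65.3% | 74.5–74.8% |
| Alpha 0.046, stratum rates up to twofold apart | 65.5–69.9% | 63.8–68.3% | 74.1–77.9% |
| Alpha 0.046, continuity correction | 50–51% | 48–49% | 61–62% |
| Alpha 0.05 (reference only) | 70% | 68% | 77% |
| Alpha 0.025 (illustrative adjustment) | 54% | 53% | 64% |

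The last three rows use equal stratum rates.

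**4. Would an unpooled z-test deliver the 80%?** Enumerated exactly at 46/23 and nominal 4.6%, its power is 78.0%, but its error rate with 6% in both arms is 7.7%. The CMH error rate in that setting is 3.2–3.6%. Part of the apparent 80% is therefore the unpooled test's excess error rate.

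**The case against.** Nothing in 10.5 is miscalculated. It names a normal-approximation test of two proportions, and the 80% follows from one such test. Sizing on a simple formula and analysing with a stratified test is common, and 10.5 never says that the 80% is CMH power. This is right as far as it goes: the fault is a mismatch between two sections, not an arithmetic error.

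The comparison also needs assumptions the documents do not supply:
- **Eye.** 10.5 uses single-eye rates, while 10.4.3 names no eye.
- **Level.** Applying 0.046 to a secondary endpoint is a choice. Under a fixed sequence the ≥2-step test could keep the full level once the primary succeeds. Even at 0.05 power is 68–77%, and having to pass the primary first would lower the overall chance of success.
- **Missing data.** Reading the cross-reference to 10.4.2 as including non-responder imputation is an interpretation. Without any missing data the ITT figure is still about 75% with equal stratum rates.
- **Strata.** With no missing data and stratum rates three- or fourfold apart, ITT power can pass 80%: one near-equal split gave 80.1% and 81.7%, another 78.1% and 79.5%. Completers stayed at about 75% or below. The ITT shortfall is therefore not unconditional.
- **ITT size.** Protocol 5.6.2 lets enrolment continue until 69 complete, so 80 is an illustration.

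Finally, no CMH test will be run. SAP 1 and 4.6 report three randomised participants and listings only. That limits the weight of the point but not its correctness.

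**Conclusion.** The concern holds and is minor. The 80% belongs to an unpooled z-formula and does not describe the stratified CMH test planned for the ≥2-step endpoint. At alpha 0.046, with 30% against 6% in both strata and no continuity correction, the chance of missing the assumed effect is about 33–34% in 69 completers and 25–36% in 80 ITT participants, not 20%. If stratum rates differ up to twofold, these become about 30–35% and 22–36%. A smaller alpha from a multiplicity adjustment would raise them further.

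Confidence is high for completers and for ITT with the planned loss counted as non-response. It is lower at the top of the ITT range, where no missing data combined with very different stratum rates could bring power to 80%. Neither document gives any power for the ≥3-step primary endpoint. No trial result is affected.

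**What to change.** Keep the sample size. Replace the power statement in Protocol 10.5 and SAP 4.5, or add one passage to the CSR, along these lines:

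> The 80% comes from the unpooled-variance z-formula for two proportions at two-sided alpha 0.046. For the CMH test of section 10.4.3, without continuity correction and with equal rates in both strata, power at alpha 0.046 is about 66–67% in 69 completers and about 64–75% in 80 ITT participants, depending on missing data, before any multiplicity adjustment. This applies to the ≥2-step endpoint with the single-eye rates of 30% and 6%. No power is given for the ≥3-step primary endpoint.

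Alternatively, report the AKST4290 rate detectable with 80% power against 6% at alpha 0.046: about 34–35% in 69 completers. With the trial stopped, the CSR passage is the realistic route.

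The cost is wording only: no extra participants and no change to any analysis, but a less favourable power figure. Changing the planned test to the unpooled z-test is not a remedy, given its 7.7% error rate. Anyone reusing the design for 80% power should plan for more participants; the pooled formula asks for 32 placebo and 64 active completers (96).

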10.6. Measures to Minimize Bias

10.6.1. Enrollment/Randomization/Masking Procedures

To minimize the potential bias at the time of randomization, the study will be double-masked and randomized in a 2:1 ratio (active 400 mg b.i.d: placebo b.i.d.) based on a block randomization schema. The randomization will be stratified by DRSS category at Baseline (moderately severe to severe NPDR). The randomization codes will be generated by a statistician who is not involved in the study other than generation and maintenance of the randomization codes.

10.6.2. Evaluation of the Success of Masking

The success of masking will be assessed based on all occurrences (intentional or unintentional) of unmasking of masked study participants or study personnel (e.g., investigators, medical providers, assessors, the Sponsor, or their representatives). All intentional and unintentional unmasking will be documented and reported.

10.6.3. Breaking the Study Mask and/or Participant Code

The study mask for either AKST4290 versus placebo can be broken for safety reasons if the information is required for the management of SAEs, severe AEs, or pregnancies. Before breaking the mask, every attempt should be made to discuss the need with the Sponsor program physician, or designee. When some degree of unmasking must occur, this should be limited to the fewest number of people on a need-to-know basis.

The investigator can obtain the AKST4290 or placebo treatment allocation for their participant through the web-based randomization system. In the rare event the web-based system is unavailable, [REDACTED] is available 24 hours/day, 7 days/week at:

Email: [REDACTED]

Toll-free: [REDACTED]

Any noted intentional or unintentional breaking of the mask should be reported to the Sponsor's study team lead and quality group. If unintentional unblinding occurs during the study, root cause analysis will be evaluated, and corrective actions implemented.

11. SOURCE DOCUMENTS AND ACCESS TO SOURCE DATA/DOCUMENTS

Each participating site will maintain appropriate medical and research records for this study, in compliance with ICH E6 R2 and regulatory and institutional requirements for the protection of confidentiality of participants. Each site will permit authorized representatives of regulatory agencies, the IRB/IEC, the Sponsor, or the Sponsor's representatives to examine (and when permitted by applicable law, to copy) clinical records for the purposes of QA reviews, audits, and evaluation of the study safety, progress, and data validity.

Source data are all information, original records of clinical findings, observations, or other activities in a clinical study necessary for the reconstruction and evaluation of the study. Examples of these original documents and data records include, but are not limited to, hospital records, clinical and office charts, laboratory notes, memoranda, participant's memory aids or evaluation checklists, pharmacy dispensing records, recorded audio tapes of counseling sessions, recorded data from automated instruments, copies or transcriptions certified after verification as being attributable, legible, accurate and complete, microfiches, photographic negatives, microfilm or magnetic media, x-rays, and participant files and records kept at the pharmacy, at the laboratories, and medico-technical departments involved in the clinical trial.

It is not acceptable for the eCRF to be the only record of a participant's participation in the study. This is to ensure that anyone who would access the participant's medical record has adequate knowledge that the participant is participating in a clinical trial. Source document templates will be developed for this study.

12. ETHICS/PROTECTION OF HUMAN SUBJECTS

12.1. Ethical Standard

The investigator will ensure that this study is conducted in full conformity with Regulations for the Protection of Human Subjects of Research codified in 45 CFR Part 46, 21 CFR Part 50, 21 CFR Part 56, ICH E6 R2, 21 CFR Part 320, Retention of Bioavailability and Bioequivalence Testing Samples (1993), and the Declaration of Helsinki.

12.2. Institutional Review Board

This protocol and any accompanying material to be provided to the participant (such as advertisements, participant information sheets, or descriptions of the study used to obtain informed consent) will be submitted by the investigator to an IRB or IEC. Approval from the IRB/IEC must be obtained before starting the study and should be documented in a letter to the investigator specifying the protocol number, protocol version, documents reviewed, and date on which the committee met and granted the approval.

All changes to the consent form will be IRB/IEC approved; a determination will be made regarding whether previously consented participants need to be re-consented.

Any modifications or amendments to the protocol must also be submitted to the IRB/IEC for approval prior to implementation.

12.3. Informed Consent Process

12.3.1. Consent Forms

Consent forms describing in detail the study agent, study procedures, and risks are given to the participant or healthcare power of attorney or equivalent legal representative, and written documentation of informed consent is required prior to any study-related procedures.

12.3.2. Consent Procedures and Documentation

It is the responsibility of the investigator or designee to obtain written informed consent form(s) (ICF) each participant participating in this study after adequate explanation of the aims, methods, objectives, and potential hazards of the study and prior to undertaking any study-related procedures.

Participants should have the opportunity to discuss the study with their family members or other advisors and the time to consider participation in the study carefully. The participants may withdraw consent at any time throughout the course of the study. The rights and welfare of the participants will be protected by emphasizing to them that the quality of their medical care will not be adversely affected if they decline to participate in this study.

The investigator or designee must utilize an IRB/IEC approved consent form that contains the elements required by ICH GCP and applicable regulatory requirements for documenting written informed consent. Each ICF will be appropriately signed and dated by the participant and the

person obtaining consent. A copy of the signed ICF will be provided to the participant. By signing the ICF, all parties agree they will complete the evaluations required by the study, unless they withdraw voluntarily or are terminated from the study for any reason.

Investigators will be expected to maintain a screening log of all potential study candidates that includes limited information about the potential candidate (e.g., date of screening).

All participants who provide consent will be assigned a unique study number. This number will be used to identify the participant throughout the clinical study and must be used on all study documentation related to the study participant. Once a number is assigned to a participant, that number will remain with that study participant and will not be reused.

If an individual's medical chart or results of diagnostic tests performed as part of an individual's regular medical care are going to be used for Screening, written informed consent must be obtained prior to review of that information in accordance with Health Insurance Portability and Accountability Act.

12.4. Participant and Data Confidentiality

Participant confidentiality is held in strict trust by the participating investigators, their staff, the Sponsor, and their agents. This confidentiality is extended to cover testing of biological samples and genetic tests in addition to the clinical information relating to participants. Therefore, the study protocol, documentation, data, and all other information generated will be held in strict confidence. No information concerning the study or data will be released to any unauthorized third party without prior written approval of the Sponsor.

The study monitor, other authorized representatives of the Sponsor, representatives of the IRB/IEC, or government regulatory agencies may inspect documents and records required to be maintained by the investigator, including but not limited to, medical records (office, clinic, or hospital) and pharmacy records for the participants in this study. The clinical study site will permit access to such records.

The investigator must assure that participants' anonymity will be strictly maintained and that their identities are protected from unauthorized parties. An identification code (i.e., not names) should be recorded on non-local laboratory samples, requisitions, and any documents submitted to the CRO, Sponsor, and/or IRB/IEC. The investigator must keep a participant log showing codes, names, and addresses for all participants screened and for all participants enrolled in the study. The study participant's contact information will be securely stored at each clinical site for internal use during the study. At the end of the study, all records will continue to be kept in a secure location for as long a period as dictated by local IRB/IEC and institutional regulations.

12.5. Future Use of Stored Specimens

With the participant's approval and as approved by local IRB/IECs, de-identified biological samples may be stored at Alkahest, or designee, for future use. These samples could be used for research and to improve treatment. Alkahest will also be provided with a code-link that will allow linking the biological specimens with the specific data from each participant, maintaining

the masking of the identity of the study participant. Participants may choose whether the Sponsor can store and use samples for further research.

During the conduct of the study, an individual participant can choose to withdraw consent to have biological specimens stored for future research.

When the study is completed, access to study data and/or samples will be managed by Alkahest. In the event Alkahest transfers ownership to another commercial Sponsor, ownership of the samples may be transferred as well.

13. DATA HANDLING AND RECORD KEEPING

13.1. Data Collection and Management Responsibilities

Data collection is the responsibility of the clinical trial staff at the site under the supervision of the site investigator. The investigator is responsible for ensuring the accuracy, completeness, and timeliness of the data reported.

Source documents provide evidence for the existence of the participant and substantiate the integrity of the data collected. Source documents are filed at the investigator's site. Data entered in the eCRFs that are transcribed from source documents must be consistent with the source documents or the discrepancies must be explained. All source documents should be completed in a neat, legible manner to ensure accurate interpretation of data. Black or blue ink is required to ensure clarity of reproduced copies. When making changes or corrections, cross out the original entry with a single line, and initial and date the change. DO NOT ERASE, OVERWRITE, OR USE CORRECTION FLUID OR TAPE ON THE ORIGINAL. The investigator may need to request previous medical records or transfer records, depending on the trial; also, current medical records must be available.

For each participant who receives the study agent or placebo, the eCRF must be completed in a timely manner. The investigator will review and approve the eCRF for each study participant after all data have been entered, the eCRFs have been source document verified, and all queries have been resolved. This also applies to records for those participant who fail to complete the study. If a participant withdraws from the study, the reason must be noted on the eCRF. If a participant is withdrawn from the study because of an AE, thorough efforts should be made to clearly document the outcome.

All data collection and recordkeeping procedures must be compliant with applicable ICH GCP.

